### Analysis of Primary Outcomes

#### *Change in $\text{VO}_{2\text{peak}}$ in lean subjects, obese subjects, and type 2 diabetes subjects groups and high-intensity group*

Change in  $\text{VO}_{2\text{peak}}$  will be calculated by subtracting baseline  $\text{VO}_{2\text{peak}}$  from final  $\text{VO}_{2\text{peak}}$  for individuals within each group. Pre- and post-test values for all four groups will be compared via repeated measures ANOVA (linear mixed model). If significant differences are identified, post-hoc t-tests will be performed to determine where these differences lie.

*Mean fold changes in beiging proteins, mRNA expression, and novel adipokines in tissue and serum*  
Mean fold change values will be calculated to determine relative changes in relevant proteins, mRNA expression and adipokines in tissue and serum for each group. Log transformation may be used to compare up and down changes in some markers. Pre- and post-test values for all four groups will be compared via repeated measures ANOVA. If significant differences are identified, post-hoc t-tests will be performed to determine where these differences lie.

Approved by  
JDC/CHS 

Conclusions will be drawn with caution due to small sample size and multiple comparisons. Regression analysis would be optimal to determine the amount of change attributable to the intervention, accounting for other factors.

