## 2. STUDY DESIGN:

### Subjects

In this section, we will provide the study design in terms of subject recruitment, exclusion criteria, visit details, exercise training program, and sample collection.

There will be two exercise training regimens. The first training regimen will determine the effects of moderate intensity endurance exercise training on scWAT in lean, healthy overweight/obese, and overweight/obese subjects with type 2 diabetes (MIT study group). The second training regimen will determine the effects of high-intensity interval training (HIT) in lean subjects (HIT study group). For both studies, the visit details, acute exercise experiments, and sample collection will be similar so they are described together.

**Subjects.** For the MIT study, there will be three groups of subjects: 1) 28 lean subjects; 2) 28 overweight or obese subjects without type 2 diabetes; and 3) 10 overweight or obese subjects with type 2 diabetes. For the HIT study, there will be 10 lean subjects. Subjects will include equal numbers of males and females, aged 25-55 years, who have been cleared for regular exercise. All subjects will be sedentary according to American College of Sports Medicine's guidelines (6). Enrollment HbA1c

[figure not shown]
Approved by  
JDC/CHS 

values will be  $\leq 5.7 \pm 0.1\%$  for lean and overweight/obese subjects and between  $6.5 \pm 0.1\%-9.0 \pm 0.1\%$  for subjects with type 2 diabetes. BMI will be between  $\geq 20 \pm 0.1$  and  $< 27 \text{ kg/m}^2$  for lean subjects,  $\geq 27$  and  $\leq 37 \pm 0.1 \text{ kg/m}^2$  for obese/overweight subjects, and  $\geq 25 \pm 0.1$  and  $\leq 37 \pm 0.1 \text{ kg/m}^2$  for subjects with type 2 diabetes.

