**VO2 Peak Testing:** At Joslin Visit 3 and Visit 5, a true VO2 peak fitness assessment will be performed with a physician and exercise physiologist present. By performing this assessment prior to the start of the exercise training program, baseline fitness will be assessed. The VO2 peak test does not evaluate the causes or mechanisms of exercise limitations. At the end of the study, participants will be reassessed using the VO2 peak testing protocol during the VO2 visit. This will be done to assess overall improvement in fitness after the 10-week exercise training program.

VO2 peak is a measure of oxygen consumption. The VO2 peak protocol allows participants to stop the test upon discomfort, as defined by volitional fatigue, and considers oxygen consumption at this point to be peak oxygen consumption. Prior to beginning the fitness assessment, the participant will have a resting electrocardiogram (ECG) performed by the study physician and will not be able to participate if any abnormalities are noted, unless this has already been obtained during Visit 2, in which case a repeat resting ECG would not be needed. During the VO2 peak test, rating of perceived exertion, and heart rate and blood pressure will be monitored. The American Heart Association's Contraindications for the VO2 testing (10) are also exclusion criteria for the study (see Appendix).

We will use a ParvoMedics Metabolic Measuring system (<http://www.parvo.com/trueone-2400/>), which also monitors heart rate. Participants will be also be monitored with an electrocardiogram and blood pressure cuff every 2 minutes. Participants will rate exercise intensity using Borg Ratings of Perceived Exertion every 2 minutes during the assessment (see Appendix for Borg scale).

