### ***3. INCLUSION / EXCLUSION CRITERIA***

Approved by  
JDC/CHS 

**Inclusion Criteria:** For the MIT study, there will be three groups of subjects: 1) 28 lean subjects; 2) 28 overweight or obese subjects without type 2 diabetes; and 3) 10 overweight or obese subjects with type 2 diabetes. For the HIT study, there will be 10 lean subjects. Subjects will include equal numbers of males and females, aged 25-55 years, who have been cleared for regular exercise. All subjects will be sedentary according to American College of Sports Medicine's guidelines (6). Enrollment HbA1c values will be  $\leq 5.7 \pm 0.1\%$  for lean and overweight/obese subjects and between  $6.5\% \pm 0.1$ - $9.0 \pm 0.1\%$  for subjects with type 2 diabetes. BMI will be  $\geq 20 \pm 0.1$  and  $< 27 \text{ kg/m}^2$  for lean subjects,  $\geq 27$  and  $\leq 37 \pm 0.1 \text{ kg/m}^2$  for obese/overweight subjects, and  $\geq 25 \pm 0.1$  and  $\leq 37 \pm 0.1 \text{ kg/m}^2$  for subjects with type 2 diabetes. The study physician will review the participants' medical records for medical and treatment history to ensure the presence of type 2 diabetes. Subjects may be enrolled in the type 2 diabetes group if they meet diagnostic criteria during the screening visit (HbA1c, fasting plasma glucose or 2-hour OGTT). Participants must be following a sedentary lifestyle defined as less than 30 minutes of moderate to intense activity 3 days per week in the last 3 months at time of study enrollment (11). Participants must be cleared for exercise, including a  $\text{VO}_2$  peak test, by their clinician or the study physician. Lean subjects who enroll in the study will be randomized to either MIT or HIT training.

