#### **4. DATA ANALYSIS / SUBJECT SELECTION**

##### **Sample Size**

Approved by  
JDC/CHS 

The initial sample size calculation of this study was done in consultation with [REDACTED] through Harvard Catalyst's biostatistical consulting service. The initial study design consisted of four study groups with a sample size of  $N = 10$  in each of the four groups. These analyses will provide an estimate of effect size. The data collected in our study are unique and sample size estimates cannot be based on previous human studies as ours is the first study to investigate how short-term exercise training impacts these novel adipokines in obesity and type 2 diabetes and few studies have evaluated scWAT beiging. However, sample size calculation in collaboration with the Harvard Catalyst biostatistician team revealed that a sample size of 9 in each group will have power of 0.85 to detect a change of 2.8 ml/kg/min in  $\text{VO}_{2\text{peak}}$ , assuming a standard deviation of that change of 2.4 based on a linear mixed models (repeated measures) analysis framework at an alpha of 0.05. Since we are interested in the effects of exercise training on changes in human adipose tissue as a primary outcome, we also calculated the sample size needed to detect changes in TGF-beta 2 mRNA expression. A sample size of 8 in each group will have similar power to detect a difference in fold change of between 1.53-1.91 (SD 0.5) over basal in adipose tissue TGF-beta 2 mRNA expression levels. The fold increase in mouse serum TGF-beta 2 after exercise was 1.56 (SD 0.5), in line with and supporting our sample size calculations based on mRNA expression. Analysis of preliminary data examining the change in UCP1 mRNA levels suggests similar magnitude of effect (i.e. fold-change on the order of 2.0 with exercise training) with a more variable response (SD of change equal to size of change), and consequently 12 subjects would be required to achieve a power of 0.88 to detect this effect at an alpha of 0.05. Conversely, with the planned sample size of 10 per group, we estimate a power of 0.80 to detect this effect size at an alpha of 0.05 in the planned analyses. We anticipate that 90% of volunteers will comply with the study protocol and, therefore, plan to include a total of 11 participants in each group.

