These original power calculations did not include an adequate number of subjects to discern differences between males and females. We have secured additional funding to determine sex-specific effects of moderate intensity exercise training on adipose tissue metabolism in lean and overweight subjects. Thus, we will increase the enrollment numbers for these two specific groups of subjects, to allow for adequate power to identify sex-specific changes in adipose tissue metabolism. The expanded groups will include: 14 lean males, 14 lean females, 14 overweight/obese males, 14 overweight/obese females, all undergoing moderate intensity exercise training.

We will evaluate changes in adipose tissue and serum as defined in the Specific Aims. Univariate analysis will be used to examine potential outliers and missing data. Categorical variables will be summarized and presented using frequencies and proportions while continuous variables will be summarized and presented using means, medians and standard deviations.

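### The randomised lean MIT versus HIT comparison leaves out the baseline value as a covariate: a modest loss of precision in a contrast that is not a stated aim

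*Combined protocol and SAP*

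**What the plan says.** Section 3, Inclusion Criteria: "Lean subjects who enroll in the study will be randomized to either MIT or HIT training". The HIT programme text in section 2 also describes the ten HIT participants as randomised. The other MIT groups are defined by BMI and diabetes status, so lean MIT versus lean HIT is the only randomised comparison.

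On numbers, section 2 says "For the HIT study, there will be 10 lean subjects". In section 4, Sample Size, "The initial study design consisted of four study groups with a sample size of" 10 in each, and MIT recruitment was later enlarged: "The expanded groups will include: 14 lean males, 14 lean females". No allocation ratio is given.

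In section 4, Analysis of Primary Outcomes, VO2peak change is final minus baseline, and "Pre- and post-test values for all four groups will be compared via repeated measures ANOVA (linear mixed model"). Then: "If significant differences are identified, post-hoc t-tests will be performed to determine where these differences lie". The beiging proteins, mRNA and adipokines get fold changes, optional log transformation, and the same ANOVA and t-tests. The section ends by remarking that "Regression analysis would be optimal to determine the amount of change attributable to the intervention, accounting for other factors", but it names no model or covariate.

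The baseline values exist. Of the pre-training VO2peak test, section 2 says "By performing this assessment prior to the start of the exercise training program, baseline fitness will be assessed", and the first adipose biopsy is taken at Visit 2.

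**The concern.** With two arms and one measurement before and after training, the group-by-time term in a repeated measures ANOVA is the two-sample t-test on change. On the log scale, fold change is also a change score. Subtracting the baseline fixes its slope at 1. When r is below 1 and the variances are similar, the best slope is r, so the change score over-corrects for chance baseline differences and carries extra noise.

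In a comparison with 10 people in one arm, even a small saving in variance is useful. Randomisation makes baseline adjustment straightforward for this contrast, which is not so for the groups that differ by design. What is at stake is the width of the MIT versus HIT confidence interval, not its validity.

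**Working it through.** **Inputs from section 4, Sample Size:** VO2peak change 2.8 ml/kg/min, SD of change 2.4, n = 9 per group, alpha 0.05, power 0.85; UCP1 SD of change equal to the change, power 0.88 at n = 12 and 0.80 at n = 10. **Arm sizes:** HIT 10; lean MIT 10 (initial design) or 28 (14 + 14, expanded). **Assumed, not in the documents:** r, two-sided testing, equal pre and post variances.

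**1. The plan's own figures.** A paired t-test on within-group change (noncentral t) gives:
- VO2peak, d = 2.8/2.4 = 1.167, n = 9: 0.864 (stated 0.85)
- UCP1, d = 1, n = 12: 0.883 (stated 0.88)
- UCP1, d = 1, n = 10: 0.803 (stated 0.80)

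A two-sample comparison of 9 v 9 with d = 1.167 gives 0.642. The VO2peak and UCP1 powers are therefore within-group powers and do not describe MIT versus HIT.

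**2. Variance ratio.** With common SD s:
- change score: 2s²(1 − r)
- baseline-adjusted: s²(1 − r²)
- ratio: (1 + r)/2
- with the cost of estimating the slope: V = [(1 + r)/2] × [1 + 1/(N − 4)], N being the two arms together.

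**3. Results for a difference of one SD of change.** In SD-of-change units the change-score standard error is √(1/n₁ + 1/n₂), which is 0.447 at 10 v 10 (18 df) and 0.368 at 28 v 10 (36 df). The power is 0.562 and 0.752. The adjusted analysis multiplies the standard error by √V and loses one df.

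| r (assumed) | V, 10 v 10 | SE | Power | V, 28 v 10 | SE | Power |
|---|---|---|---|---|---|---|
| 0.3 | 0.691 | −17% | 0.718 | 0.669 | −18% | 0.897 |
| 0.5 | 0.797 | −11% | 0.656 | 0.772 | −12% | 0.852 |
| 0.7 | 0.903 | −5% | 0.602 | 0.875 | −6% | 0.806 |
| 0.8 | 0.956 | −2% | 0.578 | 0.926 | −4% | 0.783 |
| 0.9 | 1.009 | +0.5% | 0.555 | 0.978 | −1% | 0.761 |

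Simulation at 28 v 10 (8,000 runs per r) gave variance ratios of 0.77, 0.88, 0.92 and 0.98 at r = 0.5, 0.7, 0.8 and 0.9, in agreement.

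**4. Break-even.** V = 1 when r = 2(N − 4)/(N − 3) − 1. N = 20 gives 2 × 16/17 − 1 = 0.88; N = 38 gives 2 × 34/35 − 1 = 0.94.

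**5. Where VO2peak may lie.** From SD of change = 2.4, r = 1 − 2.4²/(2 × SD²). An assumed baseline SD of 4, 6 or 8 ml/kg/min gives r = 0.82, 0.92 or 0.955, near or beyond break-even.

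**6. Adding sex as well.** If sex explains nothing further, replace 1/(N − 4) by 2/(N − 5) and drop another df. For r from 0.8 down to 0.3, power is 0.55–0.69 at 10 v 10 (0.56 with change scores) and 0.77–0.89 at 28 v 10 (0.75 with change scores).

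**The case against.** The strongest objection is that MIT versus HIT is not what the study is for. Section 1 asks whether training causes beiging and alters the metabolic phenotype of the tissue, with subaims comparing men and women. Section 2 says the HIT regimen is there to show the effects of HIT in lean subjects. The contrast arises only through a four-group ANOVA and its post-hoc tests, and the plan already promises caution over sample size and multiplicity. This stands, and it limits the importance of the point.

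Second, for VO2peak the gain may be negligible or slightly negative if people differ widely in fitness at baseline. This also stands.

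Third, a linear mixed model could be fitted with a common baseline mean for the two arms, which is close to baseline adjustment, and the plan speaks well of regression. This stands only in part: nothing excludes that model, but nothing specifies it either.

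Three stronger readings are tempting:
- *A reader might infer that the planned analysis is biased.* It is not. Change scores are unbiased under randomisation, and chance imbalance is part of the variance already counted above.
- *A reader might infer that 28 v 10 is a randomised comparison.* The documents do not settle this. Section 3 says lean enrollees are randomised, but Sample Size adds lean participants to moderate-intensity training without saying whether they were allocated alongside HIT.
- *A reader might infer that the remark about regression commits the plan to an adjusted analysis, or that all four groups should be baseline-adjusted.* The remark specifies no analysis, and the lean, overweight/obese and diabetes groups differ by design.

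**Conclusion.** The point holds as an optional refinement. The plan's one randomised contrast is analysed in a way equivalent to change scores, although a baseline value is collected for both VO2peak and the adipose markers. The cost is precision, in a contrast outside the stated aims.

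The size cannot be fixed from the documents, because neither r nor the baseline SD is given. Over the assumed range of r from 0.3 to 0.8 the saving runs from trivial to useful. VO2peak may fall at or past the trivial end. The adipose markers may gain more if their r is lower; the more variable UCP1 response hints at that, but it remains an assumption. The 28 v 10 figures apply only if all 28 lean MIT participants were randomised concurrently with HIT. The within-group analyses that carry the main aims are unaffected.

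**What to change.** Add to section 4, Analysis of Primary Outcomes:

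> For lean participants concurrently randomised to MIT or HIT, the arms are compared by regression of the post-training value (log scale for mRNA and protein markers) on arm and baseline value, or by a linear mixed model with a common baseline mean for the two arms.

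Choose one of the two forms before the data are examined. Limit this comparison to lean MIT participants who were actually randomised, and state how those added in the expansion were allocated. Do not add sex unless allocation is stratified by sex: equal numbers of men and women are planned, but no stratification is described. Keep the within-group change analyses as they are, and do not baseline-adjust across the non-randomised groups.

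The cost is one degree of freedom and one extra model, with no new data. If r is very high, power falls slightly: at 10 v 10 and r = 0.9, from 0.562 to 0.555.

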### **Local Interim Data Analysis/Data Monitoring Plan**

For this study of the effect of exercise on adipose tissue in type 2 diabetes, data safety monitoring will be performed on an ongoing basis by the Principal Investigator, [name]. In particular, the well-being and safety of subjects will be monitored closely by both the exercise physiologist and [REDACTED], who will be delegated as responsible for subject safety monitoring. Any adverse events, together with notification of appropriate action will be recorded and reported to the Principal Investigator as soon as possible. For subject safety, a screening history, physical examination, and safety check on laboratory equipment will be performed prior to the initiation of study protocol. Inclusion and exclusion criteria will be printed in each chart and will be reviewed for each subject after screening procedures are complete, prior to initiation of study procedures. Reasons for screen failure will be documented.

The Joslin Institutional Review Board reviews overall risk annually. Charts will be kept in locked offices to protect subject privacy but will be available for inspection by the safety officer upon request.

All major adverse events will be reported immediately to members of the Joslin Committee for Human Studies (CHS-IRB) whether related or unrelated to the study procedures. Minor and expected adverse events, such as those listed in the study consent form, will be reported annually to the Joslin CHS-IRB.

The Principal Investigator ([name]) is responsible for adverse event reporting and will report to the Joslin CHS (IRB) as follows:

- a. All fatal, life-threatening, or serious adverse events will be reported verbally and faxed to the IRB and to the Safety Officer as necessary within 24 hours.
- b. Unexpected adverse events will be reported verbally in real time to the CHS.
- c. Unexpected moderate or severe adverse events will be reported in writing to the CHS within 10 days of occurrence or recognition.

Study participation is voluntary, and participants may discontinue participation at any time without penalty. In the setting of expected and minor adverse events, a subject may be advised to discontinue participation upon medical grounds at the discretion of the study physician. The study will be terminated immediately should there be one major adverse event occurring in a study subject and related to study procedures.

### ***5. POSSIBLE BENEFITS:***

The overall risks to subjects for this study are minimal, and the scientific information to be gathered may be of considerable importance. There is currently very little information regarding the effects of exercise training on adipose tissue browning in subjects with obesity and type 2 diabetes. Moreover, the effects of exercise training on novel adipokines are also unknown. Understanding novel mechanisms that improve glucose homeostasis in obesity and type 2 diabetes is essential given the increasing prevalence of obesity and type 2 diabetes and these adipokines may lead to novel therapies for type 2 diabetes. Therefore, the benefits of this study appear to outweigh the risks by a considerable degree.

Approved by  
JDC/CHS

## 6. POSSIBLE RISKS:

**Risks Associated with Exercise:** There are risks associated with the exercise intervention. Although all participants will be carefully screened and cleared for exercise, there is still a remote possibility of adverse events such as abnormal blood pressure, fainting, dizziness, arrhythmia, and in very rare instances heart attack or stroke. There also exists the risk of bodily injury including injuries to muscles, ligaments, tendons, and joints. To minimize the risk of an adverse event, all participants will be pre-screened by a physician prior to participation. All participants must be cleared for exercise before they begin the intervention. Further, an assessment of physical fitness will be performed upon study enrollment, and the exercise intervention will be tailored to each participant's fitness level. Participants will exercise to percentages of heart rate reserve that are proven to be safe. In case of an emergency, arrangements for further emergent care will be made. Another risk associated with exercise is the risk of hypoglycemia. During sessions at the Joslin Diabetes Center, blood glucose measurements will be taken to prevent hypoglycemia. Prior to each exercise session, participants will be asked to check their blood sugar with a finger stick to ensure that it is at a safe level for exercise. For patients on insulin or insulin combined with oral medications, blood glucose must be at least 110 mg/dL before beginning exercise. For patients on oral medications alone, blood glucose must be at least 90 mg/dL before beginning exercise. For the VO2peak testing, higher blood glucose targets of 130 mg/dl and 110mg/dl respectively will be used. Patients will be given juice and a snack to help raise blood glucose if it is below the required value, and study staff will re-check patients' blood sugar every 15 minutes until it is above the required value.

**Risks Associated with VO2 peak testing:** It is possible that this test could cause heart abnormalities (such as irregularities of the heartbeat, lack of oxygen to the heart), dizziness or weakness. Every effort will be made to minimize these risks. Participants will be pre-screened for evidence of heart disease prior to study enrollment. They will also undergo a complete history and examination by study physician or their clinician, as well as an ECG before the treadmill test. If any abnormalities are detected that would put participants at risk during the treadmill test, they will not be allowed to perform the test or participate in the study. During this test, if participants experience 1) any uncomfortable symptoms, 2) abnormalities on the ECG monitor suggesting that a heart abnormality is occurring, or 3) significant changes in blood pressure, the test will be stopped immediately and the information will be sent to the participant's physician (see addendum and above for a list of contraindications to VO2 testing). A physician will be present in the fitness room during this procedure. Essential equipment and medical supplies are immediately available if there are any unexpected problems. The treadmill test will be performed with standardized methods and will be monitored by certified individuals. This exercise test may cause muscle soreness for 2-3 days. The risks of carefully monitored exercise tests are very low, but do rarely include non-fatal complications requiring immediate medical treatment (in less than 1 out of 10,000 tests), abnormal heartbeats requiring immediate treatment (rare, less than 1 out of 30,000 tests), or death (in less than 1 out of 150,000 tests).

**Risks of Use of Glucose:** The major risk of infusing glucose is hyperglycemia. The participant may feel thirsty. The participant should be able to rapidly clear the glucose they are given in this study during the oral glucose tolerance test.

**Risks Associated with Blood Draws and Intravenous Catheterization:** The total amount of blood drawn during the study is approximately 450 ml (or 30 tbs.). This is about less than the amount that is taken when blood is donated and should not pose any risk. Participants will be asked not to donate blood for at least 3 weeks before and after the study.

One small polyethylene catheter is placed in a peripheral vein for the withdrawal of blood samples. The participant will feel a sharp pain or sting when the needle is inserted. The potential risks of this procedure include superficial thrombophlebitis, small local hematomas, and mild local pain. In our experience, these have occurred in about 1-2% of the participants studied and resolve with local

Approved by  
JDC/CHS 

application of heat. If the symptoms have not resolved within 2 days after the application of heat, the participant will be instructed to return to the clinic for evaluation and further treatment as indicated.

**Risks Associated with Adipose Tissue Biopsies:** During the study, adipose tissue biopsies will be obtained. Participants may experience mild pain, swelling, soreness or bruising after the procedure. Local anesthesia with 1% lidocaine will be used. Participants may take acetaminophen after the procedure if required. There is a potential risk for infection. In order to avoid this, sterile procedures will be used. The area will be cleaned with betadine and sterile gloves and needles will be used. A small hematoma can collect under the skin where the needle was inserted. In order to minimize this, the perumbilical area will be selected and any areas with visible veins will be avoided. Also, pressure will be applied after the procedure.

**Risks of DXA Exam:** The DXA exam uses a small amount of X-ray radiation, so there is a very slight risk of radiation exposure. The radiation exposure is comparable to what a participant would get if he/she were in the sunshine for 3 hours or if he/she took a flight from California to New York.

